6.3.2 Efficacy Analysis

The primary analysis will be based on an intention to treat approach and will include all subjects randomized at Visit 1.

The primary efficacy endpoint will be the change in post-treatment Live Police Interaction Assessment Scores between the Virtual Reality Intervention and BE SAFE Video-Based intervention and the change in scores between the Baseline Assessment and Live Police Interaction Assessment. In the case of Cycle 2, the Baseline Assessment will be compared to the Virtual Police Interaction Assessment between the Virtual Reality Intervention and treatment-asusual groups. The study hypothesis is that participants randomly assigned to the Virtual Reality Intervention will perform better on the post-treatment Live or Virtual Police Interaction Assessment than will participants randomly assigned to the BE SAFE Video-Based intervention or treatment-as-usual condition.

The secondary endpoint will include changes in Police Interaction Knowledge Questionnaire Scores from Pre-Treatment to Post-Treatment for the Virtual Reality Intervention and BE SAFE Video-Based intervention or treatment-as-usual. The study hypothesis is that participants randomly assigned to the Virtual Reality Intervention will exhibit significantly greater improvement from Pre-Treatment to Post-Treatment on Police Interaction Knowledge Questionnaire than will participants randomly assigned to the BE SAFE Video-Based intervention condition or the treatment-as-usual condition. An additional Secondary endpoint is maintenance of learned skill improvements, indexed via the 4-week Follow-Up administration of the Virtual Police Interaction Assessment in Cycle B. The study hypothesis is that participants randomly assigned to the Virtual Reality Intervention will exhibit significantly greater Live Police Interaction Assessment Scores and skill improvement/maintenance 4-week follow-up than will participants randomly assigned to the treatment-as-usual condition.

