3.1.2 Cycle A – Laboratory-Based Efficacy Study

In the first year of the study, an efficacy study will be conducted at the Center for Autism Research. Subjects will be randomized to the VR intervention or to the video modeling control condition (with stratification, see *Study Procedure*). Subjects in each condition will undergo a baseline assessment of police interaction skills via a live role play with a study staff member and three sessions of their assigned intervention within an approximately six-week period. At the end of Visit 3, subjects' police interaction skills will be assessed via a live interaction with a police officer.

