3.1.3 Cycle B – Virtually-Based Efficacy Study

In the second year (after the completion of Cycle A), a virtually-based efficacy trial will be conducted by CHOP staff via videoconference. Subjects will be randomized to the VR intervention or to the treatment-as-usual condition (with stratification, see *Study Procedure*). Subjects in each condition will undergo a baseline assessment of police interaction skills via a novel pre-/post-intervention assessment and three sessions within an approximately six-week period. At the end of Visit 3, subjects' police interaction skills will be assessed. There will be an additional follow-up visit approximately 4 weeks post-training, for all participants, to readminister outcome measures, as an assessment of maintenance of learning.

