3.2.2 Total Number of Study Sites/Total Number of Subjects Projected

The study will be conducted at approximately two investigative sites in the United States. Cycle A of the study will be conducted at the Center for Autism Research at CHOP, while Cycle B will be conducted virtually using CHOP approved, HIPPA compliant video conferencing software.

Recruitment will stop when approximately 48 evaluable subjects complete each phase of the study. It is expected that approximately 400 subjects will be enrolled to produce 96 evaluable subjects.

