4.6 Subject Completion/Withdrawal

Subjects may withdraw from the study at any time without prejudice to their care. They may also be discontinued from the study at the discretion of the Investigator for lack of adherence to study visit schedules or procedures. The Investigator may also withdraw subjects who violate the study plan, or to protect the subject for reasons of safety or for administrative reasons. It will be documented whether or not each subject completes the pilot study. If the Investigator becomes aware of any serious, related adverse events after the subject completes or withdraws from the study, they will be recorded in the source documents and on the CRF.

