5.4.2 Police Interaction Assessments

5.4.2.1 Cycle A: Live Police Interaction Assessment

After the final VR or video modeling intervention session, all participants will be assessed via a live semi-structured interaction with a police or security officer. These interactions are specifically designed to serve as an index of behaviorally defined skills associated with effective interactions with a police officer. The police officer will be provided with a semi-structured set of prompts to use when interacting with the participant, and will rate the participant's responses. The interaction is designed with guidance from law enforcement officers with particular experience working with individuals with intellectual and developmental disabilities. The live

interaction will be video-recorded. These recordings will be coded for a set of behaviors that would encourage successful police interactions (i.e. making appropriate eye contact, etc.).

Individuals with and without ASD both experience a degree of stress/anxiety when interacting with Police Officers. Police Officers also have particular characteristics, training, and expectations which make their approaches to members of the community unique. Furthermore, Police Officer approaches and interaction are very often unexpected. Yet, Police Officer approaches to civilians are common, every day occurrences, including for individuals with ASD. As a result of these factors, it is critical that experimental measurement of effective versus ineffective interaction with Police Officers in the current study are implemented using real Police or Security Officers.

While it is important that our research participants are approached by actual Police Officers, it is also critical that risks for stress/distress and other harms are minimized. To this end, the Police Officer will be instructed to take a casual, non-accusatory approach to questioning the participant, but to otherwise follow their standard procedures in the type of scenario where they need to inquire with an individual but where that individual is not a suspect. In addition, although the Police Officers will be blinded to the experimental treatment condition of the participant, all Police Officers will be made aware that the participants may have ASD, and will be given basic information and have opportunity to ask questions and learn about what it means for someone to have ASD.

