5.4.2.2 Cycle B: Virtual Police Interaction Assessment

After the final VR intervention session, all participants will be assessed via a remote semi-structured interaction with a police or security officer avatar. Approximately 4weeks after the final VR intervention session, participants in Cycle B will be assessed once again via a remote interaction with a police or security officer. These interactions are specifically designed to serve as an index of behaviorally defined skills associated with effective interactions with a police officer. The police officer will be programmed with a semi-structured set of prompts to use when interacting with the participant, and will rate the participant's responses. The interaction is designed with guidance from law enforcement officers with particular experience working with individuals with intellectual and developmental disabilities. We will use video recordings of both the participant wearing the headset and behaviors while in the VR experience to code behaviors. These recordings will be coded for a set of both virtual and real-world behaviors that would

encourage successful police interactions (i.e. making appropriate eye contact, orienting to the virtual officer, etc.).

While it is important that our research participants are approached by simulated Police Officers, it is also critical that risks for stress/distress and other harms are minimized. To this end, the virtual reality Police Officer will take a casual, non-accusatory approach to questioning the participant, and will follow their standard procedures in the type of scenario where they need to inquire with an individual but where that individual is not a suspect.

Consistent with ethical standards in psychological research, all participants will be de-briefed immediately following the Remote Interaction Assessment. The research participant will be offered the opportunity to ask questions, and to provide their thoughts and feedback on the study procedures and practices. Research participants will also be asked to rate their experience with the remote Police Interaction, as well as the study process and procedures overall, in a formal questionnaire. Information gathered from both the interview and the questionnaire will be used to inform the researchers of how the practice is affecting research participants.

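### Intention-to-treat is declared, but subjects may be discontinued for non-adherence with no provision for a later outcome score, so the primary comparison would probably be complete-case

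*Combined protocol and SAP*

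**What the plan says.** On the analysis set, 6.3.2 is unambiguous: "The primary analysis will be based on an intention to treat approach and will include all subjects randomized at Visit 1".

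On discontinuation, 4.6 says of subjects: "They may also be discontinued from the study at the discretion of the Investigator for lack of adherence to study visit schedules or procedures". It adds: "The Investigator may also withdraw subjects who violate the study plan", alongside safety and administrative grounds. The only later data that 4.6 mentions are serious, related adverse events that come to the Investigator's attention. Section 4.5 foresees no visits outside the schedule.

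On timing of the outcome, 3.1.2 says for Cycle A: "At the end of Visit 3, subjects' police interaction skills will be assessed via a live interaction with a police officer". Section 5.4.2.1 agrees: "After the final VR or video modeling intervention session, all participants will be assessed via a live semi-structured interaction". For Cycle B, 5.4.2.2 says: "After the final VR intervention session, all participants will be assessed via a remote semi-structured interaction". Section 3.1.3 adds a repeat: "There will be an additional follow-up visit approximately 4 weeks post-training, for all participants, to readminister outcome measures". Section 6.2 makes that repeat a secondary endpoint.

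On numbers, 3.2.2 says: "Recruitment will stop when approximately 48 evaluable subjects complete each phase of the study". Evaluable is not defined.

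On method, 6.4 names a between-subjects ANOVA for the Cycle A live interaction data, gives a general list of parametric and nonparametric methods, and lists some potential covariates. No section says how a subject without a post-treatment score enters the primary analysis.

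**The concern.** An intention-to-treat analysis needs an outcome, or a stated way of handling its absence, for everyone randomised. Here the discontinuation rule removes subjects from the study and not only from the intervention, for reasons that may be related to how they would have performed. The analysis section does not say what happens to them.

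The stake is the randomised comparison itself. A complete-case contrast is biased if loss differs by arm and those lost differ from those retained. It is also biased if loss is equal but the gap between lost and retained subjects differs by arm. Recruiting on to 48 completers restores precision but not comparability.

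Unequal loss is conceivable in this design. Sessions stop on reported nausea or eye strain (9.4.2), and an adverse effect prompts a decision on continued participation (9.4.1). In Cycle A only one arm uses VR; in Cycle B the control arm meets the software only at assessments (5.3.2). Section 9.1.2 blinds confederates and coders, but does not mention the person who decides on discontinuation.

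**Working it through.** **Step 1: the text.** The plan gives no figure for post-randomisation loss, so there is none to reproduce. The sections combine as follows.

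- 6.3.2: all randomised subjects are analysed.
- 4.6: some randomised subjects may be taken out of the study before Visit 3, with no outcome assessment provided for.
- 4.5, 3.1.2, 3.1.3, 5.4.2 and Table 1: no post-treatment interaction score exists before the end of Visit 3, and no extra visit is planned.
- 6.4: an ANOVA on post-treatment scores uses only subjects who have one.

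A subject discontinued before Visit 3 is therefore promised to the analysis but would usually be absent from it.

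**Step 2: how many subjects.** Assume 10% to 20% loss after randomisation. Randomised number = 48 / (1 − loss).

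- 10%: 48 / .90 = 53.3, about 5 without a score.
- 20%: 48 / .80 = 60, so 12 without a score.

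**Step 3: how much bias.** Let p be the loss rate in an arm and g the gap, in SD, between the completers' mean and the mean of those lost. The arm's full mean is (1 − p) × completers' mean + p × mean of those lost, so the completers' mean exceeds it by p × g. With no true effect, complete-case bias = p1·g1 − p0·g0. All inputs below are assumed. The rejection rates use 24 completers per arm (1:1 allocation assumed), SE = √(2/24) = .289, a noncentral t with 46 df, and critical t 2.013 (two-sided 5%) or 2.317 (two-sided 2.5%). The 2.5% level is an assumed two-test Bonferroni correction, since 6.4 promises correction but names no method.

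| Loss, arm 1 / arm 0 | Gap, arm 1 / arm 0 (SD) | Bias (SD) | Rejection at 5% | Rejection at 2.5% |
|---|---|---|---|---|
| 10% / 5% | .5 / .5 | .10×.5 − .05×.5 = .025 | 5.1% | 2.6% |
| 10% / 10% | 1.0 / .5 | .10×1.0 − .10×.5 = .05 | 5.3% | 2.7% |
| 20% / 10% | 1.0 / 1.0 | .20×1.0 − .10×1.0 = .10 | 6.3% | 3.3% |
| 20% / 20% | 1.0 / .5 | .20×1.0 − .20×.5 = .10 | 6.3% | 3.3% |
| 25% / 5% | 1.0 / 1.0 | .25×1.0 − .05×1.0 = .20 | 10.4% | 6.0% |

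Simulating the five cases gave biases of .024, .050, .100, .099 and .200 SD, in the order of the table.

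**Step 4: does the choice of model matter?** Simulation with 29 per arm, no true effect, correlation .6 between baseline and post-treatment scores, and 25% versus 5% loss among low scorers (all assumed). ANCOVA on the completers and imputation from baseline under the same additive model gave the same estimate to rounding error.

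- Loss depends on baseline: both within .005 SD of zero, against .19 SD for the unadjusted difference.
- Loss depends on the outcome: both biased by .22 to .23 SD.

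Baseline adjustment therefore deals with the first kind of loss. Only collecting the score, or a sensitivity analysis, addresses the second.

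**The case against.** The strongest reply is that this is a short study: three paid visits over about six weeks, four visits over about ten weeks in Cycle B. Loss may be small, and four of the five illustrative cases leave the 5% error rate at or below 6.3%. The 10.4% case needs 25% against 5% loss and a full 1.0 SD gap. That stands: materiality is not demonstrated.

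Several stronger readings are tempting, and the documents do not support them.

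- *A reader might infer that 4.6 rules out later assessment.* It is silent. Discontinuation is discretionary, and 5.4.2 speaks of assessing all participants. Complete-case handling is an inference from what is left unsaid.
- *A reader might infer that 6.4 is sized on 48 completers.* It never mentions completers. It gives 48 per study, but its critical t of 1.99 and d of .74 come from 48 per group: with 94 df the two-sided 5% critical t is 1.986, and d = .743 is detectable with 95% power. Only 3.2.2 counts completers.
- *A reader might infer that a missed Visit 3 score can never be recovered.* The six-week period is approximate and no fixed window is set for Visit 3.
- *A reader might infer 76% attrition from 400 enrolled and 96 evaluable.* 3.2.2 does not separate screen failures from later losses.
- *A reader might infer that only imputation or a joint model will do.* Step 4 shows that, with a single post-treatment score as in Cycle A, baseline-adjusted ANCOVA is essentially equivalent to imputation from baseline. The choice is a preference.

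It is also fair that 6.4 contemplates covariates and that 6.1 includes change from baseline. But the listed covariates do not include the baseline interaction score, and none of this says what happens to a subject with no post-treatment score.

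**Conclusion.** The concern holds in this form: the stated analysis set and the stated discontinuation rule do not fit together, and nothing in the plan bridges them. Followed as written, the primary result would probably be a complete-case comparison labelled intention-to-treat.

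That conclusion rests on the text. The size does not: loss rates, gaps, 1:1 allocation and the baseline correlation are all assumptions, and neither size nor direction can be predicted from the documents. The illustrated range, .025 to about .2 SD, is immaterial at the low end. Differential loss is plausible but not shown. The plan should be changed because the remedy is cheap and the first part of it has to be in place while subjects are being followed.

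**What to change.** **(a) Section 4.6.** State that non-adherence or a study-plan violation alone ends neither participation for outcome purposes nor the invitation to the Visit 3 assessment and, in Cycle B, the 4-week assessment. Limit this to subjects for whom the assessment remains permitted under the protocol, because the Cycle B assessments involve further headset use. Leave safety withdrawals and stopping rules unchanged.

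**(b) Section 6.3.2.** Analyse subjects as assigned regardless of adherence, adjusting for the baseline interaction score already collected. ANCOVA, multiple imputation or a likelihood-based model would serve, at the statistician's choice; if imputing in Cycle B, use the 4-week score as an auxiliary variable. In a joint model for Cycle A, give baseline and post-treatment scores separate means and variances, since the baseline is a staff role play. Add one missing-not-at-random sensitivity analysis covering all randomised subjects, for example delta-adjusted imputation by arm.

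**(c) Reporting.** Give the numbers randomised and lost by arm, with reasons, and define evaluable in 3.2.2.

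**Cost.** Wording in these sections, a few extra assessments (officer time in Cycle A, remote headset sessions in Cycle B) and modest analysis work. Including non-adherent subjects may dilute the estimated effect somewhat. Some will decline the assessment, so the sensitivity analysis is still needed.

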5.4 Efficacy Evaluations

5.4.1 Baseline Assessment

5.4.1.1 Cycle A

Before beginning the first VR or video modeling intervention session, all participants will complete a baseline assessment of police interactions skills via a live role play of a police interaction with a study staff member. These interactions are designed to measure each participant's ability to interact with a police officer prior to completing either intervention. The study staff member will be provided with a semi-structured set of prompts to use when interacting with the participant. The interaction is designed with guidance from law enforcement officers with particular experience working with individuals with intellectual and developmental disabilities. The live interaction will be video-recorded via a videoconference platform. These recordings will be coded for a set of behaviors that would encourage successful police interactions (i.e.: making appropriate eye contact, etc.)

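### In Cycle A the within-arm change from the Baseline Assessment to the Live Police Interaction Assessment cannot be read as improvement, because the test changes between the two time points, yet 6.3.2 lists it in the primary endpoint

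*Combined protocol and SAP*

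**What the plan says.** Section 6.3.2 gives the Cycle A primary efficacy endpoint two components. The first is the "change in post-treatment Live Police Interaction Assessment Scores between the Virtual Reality Intervention and BE SAFE Video-Based intervention". The second is "the change in scores between the Baseline Assessment and Live Police Interaction Assessment". The first names the two arms; the second names none.

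The assessments are described separately:

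- **Baseline (5.4.1.1):** a "baseline assessment of police interactions skills via a live role play of a police interaction with a study staff member".
- **Post-treatment (3.1.2 and 5.4.2.1):** "At the end of Visit 3, subjects' police interaction skills will be assessed via a live interaction with a police officer". Section 5.4.2.1 widens this to a police or security officer. It adds that the officer "will rate the participant's responses", and no matching rating by the staff member is described at baseline.

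Section 5.4.2.1 explains why real officers are used at outcome: "Police Officers also have particular characteristics, training, and expectations which make their approaches to members of the community unique". It regards their use as critical to the measurement. The documents describe no calibration or equivalence work linking the role play to the officer interaction.

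Section 6.1 differs from 6.3.2. It lists a change from baseline only for the Virtual assessment, and it names only treatment-as-usual as comparator, although the Cycle A control is video modeling (5.3.1).

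**The concern.** A change score measures improvement only if the same thing is measured twice. Here the interaction partner changes from a staff member to an officer for every subject, whatever the training. If officers are more stressful to deal with, scores may fall with no loss of skill. If officers are easier or more practised partners, scores may rise with no gain.

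Because the change component carries no arm contrast, a pre/post gain in the VR arm alone could be reported as a primary result while following 6.3.2 as written. The background to the power section points the same way: 6.4 cites a within-group pre/post effect (d = .63) from the most relevant earlier study. At stake is whether a primary result of the form that the VR arm improved would mean anything in Cycle A.

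**Working it through.** **Inputs from the documents.** 48 subjects per study (6.4), taken as 24 per arm; the allocation ratio is not stated, so 1:1 is assumed. d = .74, critical t 1.99 and N = 48 per group (6.4).

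**Assumed inputs.** Equal SDs at both time points (set to 1), a correlation r between the two tests, and a test shift common to all subjects. None of these is in the documents, so ranges are shown.

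**The plan's own figure.** Section 6.4 gives no figure for a change score. Its between-group figure reproduces with 48 per arm and two-sided 5%: df = 94, critical t = 1.9855, detectable d = 0.7435 at 95% power (the power and alpha are inferred). With 24 per arm, power at d = 0.74 is 0.71. The mismatch between 48 per group and 48 per study is a separate matter; 24 per arm is used below.

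**Step 1: within-arm change, no training effect.** The SE of the mean change is sqrt(2(1 − r)/n). With n = 24 and r = 0.3 this is sqrt(1.4/24) = 0.242 SD. Multiplying by t(0.975, 23 df) = 2.069 gives 0.50 SD, the smallest observed mean shift that is significant. At other correlations:

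- r = 0.2: sqrt(1.6/24) × 2.069 = 0.53 SD
- r = 0.5: sqrt(1.0/24) × 2.069 = 0.42 SD
- r = 0.8: sqrt(0.4/24) × 2.069 = 0.27 SD

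Simulation (20,000 runs, 24 per arm) agrees. With a 0.5 SD test shift and no training effect, the VR-arm pre/post test rejects in 46%, 65% and 96% of trials at r = 0.2, 0.5 and 0.8, against a nominal 5%. In the other direction, a true gain of 0.74 SD with a shift of −0.5 SD leaves a mean change of 0.74 − 0.50 = 0.24 SD.

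**Step 2: between-arm difference in change.** A shift s common to both arms cancels: (gain in VR + s) − (gain in control + s) contains no s. In the same simulation the type I error stays at about 5% and the estimate at about 0.74 for shifts of −0.5, 0 and +0.5 SD. The comparison of Visit 3 scores alone is equally unbiased.

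**Step 3: precision of the valid between-arm analyses.** Relative to the Visit 3 score alone, the SE is multiplied by sqrt(2(1 − r)) for the change score and by sqrt(1 − r²) for ANCOVA on the baseline score. Power is at d = 0.74, 24 per arm, two-sided 5%; the ANCOVA figures do not deduct the one degree of freedom for the covariate.

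| r | SE ratio, change | SE ratio, ANCOVA | Power, Visit 3 only | Power, change | Power, ANCOVA |
|---|---|---|---|---|---|
| 0.2 | 1.26 | 0.98 | 0.71 | 0.51 | 0.73 |
| 0.3 | 1.18 | 0.95 | 0.71 | 0.56 | 0.75 |
| 0.5 | 1.00 | 0.87 | 0.71 | 0.71 | 0.83 |
| 0.7 | 0.77 | 0.71 | 0.71 | 0.90 | 0.94 |
| 0.8 | 0.63 | 0.60 | 0.71 | 0.98 | 0.99 |

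The change score loses to the Visit 3 score below r = 0.5 and beats it above. ANCOVA is at least as good as either throughout this range, and it does not need the two tests to be on a common footing.

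**The case against.** The strongest reply is that the trial's claim is comparative. The objective in 2.1 is improvement relative to a comparator. The hypothesis in 6.3.2 is between-arm on the post-treatment score. The only Cycle A model in 6.4 is an ANOVA with Group as the between-subjects factor and no time factor. No within-arm test is written down, and the sentence in 6.3.2 on the second cycle does set its baseline comparison between groups. On this view the missing contrast is loose wording.

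The two tests also have much in common. Both use semi-structured prompts, are designed with law-enforcement guidance and are video-recorded, and their recordings are coded for behaviors described in nearly the same words (5.4.1.1, 5.4.2.1). Confederates and coders are blinded (9.1.2). Section 6.1 does not list the Baseline-to-Live change at all.

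Most of this stands, and it limits the point. A reader might infer that Cycle A cannot show improvement at all, or that its randomised comparison is biased. The documents do not support that: both arms take the same two tests, so a common shift cancels. A reader might also infer that the officer's rating puts the two scores on different scales, but nothing says that the rating enters the score. Nor do the documents say that the role play measures something different; 5.4.2.1 argues for real officers at outcome, and the non-equivalence is an inference from that argument. Finally, no document supports a correlation below 0.5 over one above it.

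The reply does not rescue the within-arm reading. Shared coding does not remove a shift caused by a different interaction partner, and 6.3.2 leaves that reading open within the primary endpoint.

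**Conclusion.** The point holds for the within-arm change in Cycle A. As 6.3.2 is written, that change is part of the primary endpoint, has no arm contrast, and confounds change in skill with change of test. With 24 per arm and r = 0.3, a test shift of about 0.50 SD suffices for significance without any training effect; over r = 0.2 to 0.8 the threshold runs from 0.53 to 0.27 SD. These figures rest on 1:1 allocation, equal SDs, and an assumed shift and correlation. They show what could happen; they do not estimate what will.

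Improvement relative to BE SAFE remains testable without bias from the change of test, provided that the change acts equally in both arms. If one arm's training interacted with the officer setting, that would be part of the effect on the officer test. Between the valid analyses the issue is precision, and its direction depends on a correlation that the documents do not give.

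**What to change.** In 6.3.2, for Cycle A:

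- Delete the Baseline-to-Live change as a primary quantity.
- Make the single primary endpoint the between-arm difference (VR against BE SAFE) in the Visit 3 Live score, analysed by ANCOVA with the baseline role-play score as a prespecified covariate. Add that score to the covariates in 6.4, which do not now include it.
- State that no within-arm improvement claim is made in Cycle A.
- State whether the officer's rating enters the Live score.

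Reconcile 6.1 with 6.3.2, so that both name the same Cycle A endpoint and the video modeling comparator.

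The cost is wording only: the role play is already scheduled, so no visit or measurement is added. The downside is that the sponsor gives up a within-arm improvement statement for Cycle A.
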